4.2 CONCOMITANT THERAPY, RESTRICTIONS, AND RESCUE TREATMENT

4.2.1 Rescue medication, emergency procedures, and additional treatment(s)

Concomitant therapies should be limited to those essential for the non-gastrointestinal care of the patient. All concomitant medications and the reason(s) for use will be documented throughout the course of the study.

In case of infusion reactions emerging during or after infusion of BI 655066/ABBV-066 (risankizumab), the investigator should consider in accordance with severity of the reaction and local standard of care to

- immediately interrupt the infusion
- treat with systemic anti-histamines and intravenous steroids

Based on patient's clinical course and medical judgment, the infusion may be re-initiated in case of mild or moderate reactions (according to RCTC grading in [Appendix 10.3](#)) at

lower speed with gradual increase to complete the infusion as detailed in the Instructions for Preparation and Handling of BI 655066/ABBV-066 (risankizumab) in the Investigator Site File.

In case of adverse events in need of treatment, symptomatic therapy according to the judgment of the investigator will be permitted. All concomitant and/or rescue therapies will be recorded on the appropriate pages of the eCRF.

There are no special emergency procedures to be followed.

4.2.2 Restrictions

4.2.2.1 Restrictions regarding concomitant treatment

Medications	Restriction time period
Investigational products	4 weeks or 5 half-lives, whichever is greater
5-ASA compounds.	
Rectal 5-ASA compounds are not permitted during the study and must have been discontinued at least 4 weeks prior to visit 2.Oral 5-ASA compounds must have been at a stable dose for at least 4 weeks prior to visit 2.If oral 5-ASA compounds were recently discontinued, they must have been discontinued at least 4 weeks prior to visit 2.

Immunomodulators	
Patients receiving chronic (i.e., ≥ 12 weeks) treatment with AZA, 6-MP, or MTX prior to visit 2 must have been on a stable dose for at least 4 weeks prior to visit 2 and must continue on this same dose during the study. Patients who have discontinued therapy with AZA, 6-MP, or MTX must have stopped the medication at least 4 weeks prior to visit 2 to be considered eligible for randomisation.
 
Patients must not have received therapy with other known immunomodulators (e.g., 6-thioguanine [6-TG], cyclosporine, tacrolimus, sirolimus, pentoxifylline, or mycophenolate mofetil) or experimental agents (e.g., granulocyte macrophage – colony stimulating factor [GM-CSF]) within 8 weeks or 5 half-lives of agent from visit 2, whichever is longer.

monoclonal antibodies or anti-TNF agents	Patients must not have received therapy ≤ 8 weeks or 5 half-lives (whichever is longer) from visit 2 and during study treatment period.

4.2.2.1 Restrictions regarding concomitant treatment (cont.)

Medications	Restriction time period
Systemic corticosteroids (eg, prednisone, budesonide)	
 Parenteral (SC, IM, or IV) or rectal corticosteroids are not permitted during the study and must not have been used within a 4-week period prior to visit 2. Oral corticosteroids must be at a prednisone-equivalent dose of ≤ 20 mg/day, or ≤ 6 mg/day of budesonide, and have been at a stable dose for at least 4 weeks prior to visit 2. If oral corticosteroids were recently discontinued, discontinuation must have been completed at least 3 weeks prior to visit 2.

Crohn's disease-specific antibiotics	If using a Crohn's disease-specific antibiotic for treatment of Crohn's disease, patients must have been using the antibiotic for at least 4 weeks before visit 2 at a stable dose. If not currently using a Crohn's disease-specific antibiotic, the stop date must have been at least 4 weeks prior to visit 2.
Opioids	Patients with regular daily opioid use over the past 3 months before screening are excluded due to the interference of such medication with key efficacy endpoints (CDAI)
Live or attenuated vaccines (during study or 140 days after last dose of study drug)	
• live attenuated influenza (intranasal)• herpes zoster• rotavirus• varicella (chicken pox)• measles-mumps-rubella (MMR) or measles mumps rubella varicella (MMRV)• oral polio vaccine (OPV)• smallpox• yellow fever• Bacille Calmette-Guérin (BCG)• oral typhoid

Tapering of corticosteroids

The tapering of prednisone dosage or equivalent (see [Appendix 10.2](#)) of other systemic corticosteroids is requested for patients achieving clinical remission the first time while on treatment with BI 655066. In such patients steroids must be tapered at a maximum rate of 2.5 mg per week to a dosage of 0. If a patient experiences a loss of clinical response (decrease in CDAI < 100 points from baseline on 2 consecutive visits) during steroid tapering, the dosage of prednisone may be increased back to the dosage used at study entry.

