3.3.1 Main diagnosis for study entry

3.3.2 Inclusion criteria

1. Patients with Crohn's disease, who have successfully completed the preceding trial 1311.6. Successful treatment is defined as:
 - Completion of period 2 in 1311.6 with a clinical response (drop in CDAI from baseline by ≥ 100) but no remission (CDAI < 150) at Visit E1; or
 - Completion of period 3 in 1311.6 with a clinical response (drop in CDAI from baseline by ≥ 100) **and** / or remission (CDAI < 150) at Visit E5; or
 - Completion of period 2 or 3 in 1311.6 per protocol with a clinical response or remission before initiation of 1311.20/M15-989 may roll-over either directly if that response/remission is maintained or through an open-label i.v. re-induction phase if they have lost their previous response/remission.(for more details see Section 3.1)

2. Female patients:
 - a. Women of childbearing potential (not surgically sterilized and between menarche and 1 year postmenopause), that, if sexually active agree to use one of the appropriate medically accepted methods of birth control in addition to the consistent and correct use of a condom from date of screening until 20 weeks after last administration of study medication. Medically accepted methods of contraception are: ethinyl estradiol containing contraceptives, diaphragm with spermicide substance, and intra-uterine-device, or
 - b. Surgically sterilized female patients with documentation of prior hysterectomy, tubal ligation or complete bilateral oophorectomy, or
 - c. Postmenopausal women with postmenopausal is defined as permanent cessation \geq 1 year of previously occurring menses, and
 - d. Negative serum β -Human Chorionic Gonadotrophin (β -HCG) test at screening and urine pregnancy test prior to randomization.
- Male patients:
 - a. Who are documented to be sterile, or
 - b. Who consistently and correctly use effective method of contraception (i.e., condoms) during the study and 20-weeks after last administration of study medication.
3. Be able to adhere to the study visit schedule and other protocol requirements.

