5. VARIABLES AND THEIR ASSESSMENT

5.1 EFFICACY - PHARMACODYNAMICS

5.1.1 Endpoint of efficacy

Efficacy endpoints are:

- Clinical remission by visit, defined as a CDAI score of < 150.
- Clinical response by visit, defined by either a CDAI score of < 150 or a CDAI reduction from baseline of at least 100 points.
- PRO-2 remission by visit, defined by a PRO-2 score of < 75
- PRO-2 response by visit, defined as a decrease from baseline of 50 points or more.
- CDEIS remission by visit, defined as a score of 4 or less (for patients with initial isolated ileitis a score of 2 or less)
- CDEIS response by visit, defined as a score of 7 or less (for patients with initial isolated ileitis > 50% reduction from baseline).
- Mucosal healing by visit, defined as the absence of mucosal ulceration.
- Deep remission by visit, defined as clinical remission and endoscopic remission (CDEIS).
- Change from baseline in CDAI scores by visit.
- Change from baseline in PRO-2 scores by visit.
- Change in CDEIS by visit.
- Change in SES-CD by visit.
- CDEIS percentage change from baseline by visit.
- SES-CD percentage change from baseline by visit.
- Reduction of 75% in CDEIS scores from baseline by visit.
- Reduction of 75% in SES-CD scores from baseline by visit.
- Change from baseline in stool frequency by visit based on patient diary.
- Stool consistency by visit based on patient diary.
- Change from baseline in abdominal pain score by visit based on patient diary and scored, with possible answers none, mild, moderate and severe.
- Change from baseline in IBDQ scores by visit.
- Change from baseline in CRP and fecal calprotectin profile by visit.
- Reduction in the number of draining fistulas in patients with draining fistulas at baseline.

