7.2 NULL AND ALTERNATIVE HYPOTHESES

There is no formal statistical hypothesis test planned.

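### The steroid re-increase trigger omits the CDAI < 150 limb of the response endpoint, and two maintenance visits after the start do not fit inside a taper at the maximum rate

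*Protocol*

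**What the plan says.** Under the tapering paragraph of Protocol 4.2.2.1, a steroid taper "is requested for patients achieving clinical remission the first time while on treatment with BI 655066". On speed: "In such patients steroids must be tapered at a maximum rate of 2.5 mg per week to a dosage of 0". If the patient then shows "loss of clinical response (decrease in CDAI < 100 points from baseline on 2 consecutive visits) during steroid tapering", the prednisone dose may go back up to its level at study entry. The same section limits the dose at entry: "Oral corticosteroids must be at a prednisone-equivalent dose of ≤ 20 mg/day, or ≤ 6 mg/day of budesonide". Section 5.1.2 asks for a stable dose until remission.

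Elsewhere the protocol defines response in two ways:

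- Section 5.1.1, repeated in SAP 4.3.2: "Clinical response by visit, defined by either a CDAI score of < 150 or a CDAI reduction from baseline of at least 100 points". Remission is "Clinical remission by visit, defined as a CDAI score of < 150".
- Section 3.3.2 uses the drop alone and names remission beside it as a further route: "Completion of period 3 in 1311.6 with a clinical response (drop in CDAI from baseline by ≥ 100".

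In Flow Charts 1 and 2, CDAI is measured every 8 weeks from V2, with windows of ±7 days. In Flow Chart 3, V2 to V5 are 4 weeks apart (±5 days at V3 and V4, ±7 at V2 and V5), and visits are 8-weekly after that. Section 6.1 allows unscheduled visits for repeat laboratory tests or safety follow-up, but schedules no CDAI at them.

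**The concern.** The taper is meant for patients who have reached remission, yet the rule for reversing it ignores remission and looks only at the size of the drop. A patient can thus be a responder for the endpoint and a lost responder for the taper rule at the same visit. The rule also asks for two visits in a row while the taper is running, and the maintenance schedule is sparse compared with the permitted taper speed.

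At stake is whether sites can apply the rule uniformly. Steroid dose bears on CDAI, and Section 3.2 names durability of response among the aims. SAP 4.3.3 has an exploratory endpoint combining at least 90 days off corticosteroids with symptom targets. The SAP's non-responder imputation (9.1.2) covers missing values only and says nothing about CDAI observed after a re-increase.

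**Working it through.** The plan states no taper length or visit count for this rule, so there is no figure of its own to reproduce. The check is direct arithmetic.

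**1. Where remission and loss of response overlap.** Let B be the 1311.6 baseline CDAI and C the current CDAI. Remission: C < 150. Loss under 4.2.2.1: B − C < 100, so C > B − 100. Both hold when B − 100 < C < 150, which needs B < 250 (248 or less in whole points). The documents give no baseline range, so these baselines are assumed:

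| Baseline | Remission values counted as loss |
|---|---|
| 180 | 81–149 |
| 200 | 101–149 |
| 220 | 121–149 |
| 230 | 131–149 |
| 240 | 141–149 |
| 249 or more | none |

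Example: B = 230, C = 140 gives a drop of 90. That is remission and response under 5.1.1, and loss under 4.2.2.1 if repeated at the next visit.

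**2. Who can be in the overlap.** A patient admitted as a responder without remission had C ≥ 150 and B − C ≥ 100, so B ≥ 250. Such a patient is outside the overlap. Conversely, a patient with B < 250 who qualified on a drop of at least 100 had C < 150. Every exposed patient was therefore already in remission in 1311.6.

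**3. Length of a taper at the maximum rate.** Weeks = dose / 2.5. From 20 mg: 20/2.5 = 8. From 15, 10 and 5 mg: 6, 4 and 2. Each is one week shorter if the first cut is made on day 0. Budesonide has no conversion factor in Appendix 10.2, so its taper length cannot be computed.

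**4. Visits after a start on maintenance (V2 onward in Flow Charts 1 and 2, V5 onward in Flow Chart 3).** The first later visit is at week 8 (earliest 8 − 2 = 6). The second is at week 16; with ±7 days at both ends the range is 16 − 2 = 14 to 16 + 2 = 18. The smallest gap after an 8-week taper is 14 − 8 = 6 weeks. For both visits to fall inside a taper from 20 mg, the average rate must be at most 20/16 = 1.25 mg/week, or 20/14 = 1.43 mg/week with the most favourable windows.

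**5. Starts off the 8-week grid.** In Flow Chart 3, a start at V3 puts V4 and V5 at 4 and 8 weeks (V5: 56 ± 12 days, or 6.3 to 9.7 weeks). That just fits a full-rate taper from 20 mg, but not from 15 mg (6 weeks). A start at V4 puts the second visit at 12 weeks (10.3 to 13.7), which does not fit. A start at screening V1 by a patient who attends V1.1 is followed by visits at week 1 and week 4 or 6 (Flow Charts 1 and 2), which do fit; this precedes dosing in the trial.

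**6. Whether the start visit counts.** The text does not say. If B ≥ 250 and the patient starts in remission, the drop exceeds 100, so the start visit cannot count as loss; a later relapse needs weeks 8 and 16. If B < 250 and the drop at the start is below 100, the start visit and week 8 (earliest 6) could complete the pair inside a full-rate 20 mg taper, with the patient in remission throughout.

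**7. Which baseline.** The rule names none. Section 3.1 judges response after re-induction against the 1311.6 baseline; Section 6.2.2 judges it against entry to this trial.

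**The case against.** The strongest reply has four parts.

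- *The rule is consistent with the protocol.* Section 3.3.2 defines response as a drop of at least 100, and the taper rule is its exact complement. This stands: the protocol carries two definitions, and the rule conflicts with one. It does not remove the conflict with 5.1.1 and SAP 4.3.2.
- *Loss in remission is nearly ruled out.* The taper is tied to first remission on drug, and anyone with a baseline below 250 had already reached it in 1311.6. This narrows the exposure to remitters from 1311.6 whose steroids are tapered here. A reader might infer that every patient with a low baseline is affected; the documents do not support that, nor do they show that nobody is.
- *2.5 mg/week is a ceiling.* Slower tapers comply and can contain two visits, as can the V3 start in Flow Chart 3. A reader might infer that the condition can never be met in a full-rate taper; the re-induction visits show otherwise. For a relapse in a full-rate taper begun on maintenance visits by a patient with baseline of 250 or more, the conflict remains.
- *Little depends on it.* Re-increase is optional, steroid changes are recorded, and the 90-day endpoint uses medication records rather than this trigger. Section 7.2 says "There is no formal statistical hypothesis test planned", and 3.3.4.1 provides separately for stopping study treatment for lack of efficacy. All this limits the consequence. The provision in 3.3.4.1 uses a different condition and does not settle the taper rule.

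**Conclusion.** Two inconsistencies hold. First, the trigger omits the CDAI < 150 limb of the endpoint definition, so a patient with a 1311.6 baseline below 250 can be in remission and meet the loss definition. This is confined to patients already in remission in 1311.6 and tapered in this trial, and their number is unknown. Second, at the maximum rate from at most 20 mg/day, a taper begun at a maintenance visit ends at least 6 weeks before the second later visit. A patient with baseline of 250 or more who starts in remission and then relapses cannot meet the condition in that time.

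This assumes prednisone-equivalent dosing, scheduled CDAI visits only, and the 1311.6 baseline as reference. A reader might go further and conclude that the rule biases the CDAI durability summaries or the 90-day steroid-free endpoint. The documents do not show this: they do not say how many of the roughly 60 patients are on steroids or would be tapered, and the analyses are descriptive or exploratory. The rule should be corrected because it does not operate as written on the main visit schedule at the stated maximum rate, not because a distortion of results has been demonstrated.

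**What to change.** - Reconcile 4.2.2.1 with 5.1.1 and 3.3.2 so that one definition of clinical response, and of its loss, applies. State which baseline it uses, and resolve the difference between 3.1 and 6.2.2.
- Reconcile the requirement for two visits in a row within the taper with the stated maximum rate and the 8-week visit spacing. Say whether the visit at which the taper starts counts.

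The clinical content is for the sponsor's clinical team to decide. The cost is a protocol clarification or a letter to sites; aligning the definitions needs no new visits or data.

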4.3 TREATMENT COMPLIANCE

Dose administration compliance will be assured by administration of all study medication under supervision of the investigating physician or a designee at the research site. The measured plasma concentrations will provide additional information about compliance.

5. VARIABLES AND THEIR ASSESSMENT

5.1 EFFICACY - PHARMACODYNAMICS

5.1.1 Endpoint of efficacy

Efficacy endpoints are:

- Clinical remission by visit, defined as a CDAI score of < 150.
- Clinical response by visit, defined by either a CDAI score of < 150 or a CDAI reduction from baseline of at least 100 points.
- PRO-2 remission by visit, defined by a PRO-2 score of < 75
- PRO-2 response by visit, defined as a decrease from baseline of 50 points or more.
- CDEIS remission by visit, defined as a score of 4 or less (for patients with initial isolated ileitis a score of 2 or less)
- CDEIS response by visit, defined as a score of 7 or less (for patients with initial isolated ileitis > 50% reduction from baseline).
- Mucosal healing by visit, defined as the absence of mucosal ulceration.
- Deep remission by visit, defined as clinical remission and endoscopic remission (CDEIS).
- Change from baseline in CDAI scores by visit.
- Change from baseline in PRO-2 scores by visit.
- Change in CDEIS by visit.
- Change in SES-CD by visit.
- CDEIS percentage change from baseline by visit.
- SES-CD percentage change from baseline by visit.
- Reduction of 75% in CDEIS scores from baseline by visit.
- Reduction of 75% in SES-CD scores from baseline by visit.
- Change from baseline in stool frequency by visit based on patient diary.
- Stool consistency by visit based on patient diary.
- Change from baseline in abdominal pain score by visit based on patient diary and scored, with possible answers none, mild, moderate and severe.
- Change from baseline in IBDQ scores by visit.
- Change from baseline in CRP and fecal calprotectin profile by visit.
- Reduction in the number of draining fistulas in patients with draining fistulas at baseline.

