6.4 Definition of Visit Windows

Since subjects do not always adhere to the study visit schedule, the following rules will be applied to assign actual visits to protocol-specified visits including early termination visits. For each study visit mentioned in the protocol, a nominal or target day will be selected to represent the corresponding visit along with a window around the target day. Windows will be selected in a non-overlapping fashion so that a date collected on the case

report form (CRF) does not correspond to multiple visit windows. Moreover, windows will not discard any post-baseline measurement recorded on the CRF. If a subject had 2 or more actual visits in one visit window, the visit closest to the target will be used as the study visit for that window. If two visits are equidistant from the target day, then the later visit will be used for reporting.

The visit windows and the target/nominal day for each study visit are shown in the tables below. The visit windows defined below will be based on relative days to either first dose on IV or first dose on SC.

Table 1. Windows for subcutaneous injection period for ITT_SC (SA_SC) population, using for Vital sign, Lab Values, Fistula exam, CDAI, Review patient diary (PRO data).

Nominal Visit Week^d	Lower Bound	Nominal Day	Upper Bound
0	-999	1 ^a	1
8	2	57	85
X ^c	$1 + 7*(X - 4) + 1$	$1 + 7*X$	$1 + 7*(X + 4)$
200	1374	1401	9999 ^b

- a. Day of first dose of study drug for subcutaneous injection.
- b. It is minimum of (the last dose date + 140 days, the first dose date of Study M16-000 sub-Study 3) for the subjects who entered the Study M16-000 sub-Study 3; otherwise it is the last dose date +140 days.
- c. $X = 8*i$, $i = 2, \dots, 24$.
- d. Nominal visit week is a transformation of the protocol-specified week. For the patients' schedule following the Flow Chart 1, nominal visit week = protocol-specified week – 4. For the patients' schedule following the Flow Chart 2, nominal visit week = protocol-specified week – 6. For the patients' schedule following the Flow Chart 3 (only for subcutaneous injection period), nominal visit week = protocol-specified week – 16.

Table 2. Windows for subcutaneous injection period for ITT_SC population, using for CDEIS and SES-CD.

Nominal Visit Week ^c	Lower Bound	Nominal Day	Upper Bound
0	-999	1 ^a	1
48	2	337	533
104	534	729	897
152	898	1065	1233
200	1234	1401	9999 ^b

- a. Day of first dose of study drug for subcutaneous injection.

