9.4 Other Efficacy Analysis

There are no other efficacy analyses.

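### Six of the 22 efficacy endpoints in protocol 5.1.1, including draining fistulas and the 75% endoscopic reductions, are missing from the SAP with no reason recorded

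*Protocol*

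**What the plan says.** Protocol 5.1.1 opens its list with "Efficacy endpoints are" and gives 22 items. They include "CDEIS percentage change from baseline by visit" with a matching item for SES-CD; further down, "Reduction of 75% in CDEIS scores from baseline by visit", again with an SES-CD counterpart; a stool-consistency item taken from the diary; and, last in the list, "Reduction in the number of draining fistulas in patients with draining fistulas at baseline". Protocol 5.1.2 also defines a fistula response as a fall of at least 50% in the number of draining fistulas.

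Protocol 7.3.2 names no secondary efficacy analysis. It says the other efficacy endpoints will be tabulated descriptively by visit, and it allows the SAP to define further ones.

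The SAP lists 20 secondary endpoints (4.3.2) and 6 exploratory endpoints (4.3.3). Section 9.3 analyses the first set and 9.5 the second. Section 9.4 states "There are no other efficacy analyses". Section 11.0 says only that the plan was adapted from the previous sponsor's analysis plan of 15 July 2016 and follows the present sponsor's conventions. It names no removed endpoint.

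Fistula data have not left the SAP altogether. The caption of Table 1 in 6.4 reads "Windows for subcutaneous injection period for ITT_SC (SA_SC) population, using for Vital sign, Lab Values, Fistula exam", Table 6 does the same for the IV period, and 7.1 tabulates draining fistulas at baseline.

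**The concern.** A protocol endpoint that the SAP does not list will not be programmed. The protocol contemplates additions in the SAP, not deletions, so a reader comparing the two documents would expect each missing endpoint to be explained.

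The setting makes the silence matter. Treatment is open label and the dose is visible in the database (protocol 4.1.5.1). The SAP is dated 15 July 2019 and describes treatment and the monitoring committee's reviews in the past tense (SAP 4.2, 4.5). When endpoints disappear at that stage without a reason, a reader cannot tell an editorial slip from a choice made with results in view. Two kinds of result are at stake: any post-baseline fistula outcome, and the proportion of all treated patients with a large relative endoscopic improvement.

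**Working it through.** The check is a one-to-one match of the lists; the documents state no count of their own.

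**Inputs**
- Protocol 5.1.1: 22 bullets.
- SAP 4.3.2: 20 bullets.
- SAP 4.3.3: 6 bullets.

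**Protocol items found in SAP 4.3.2**
- Clinical remission and response, PRO-2 remission and response, CDEIS remission and response, mucosal healing, deep remission: 8.
- Change in CDAI, PRO-2, CDEIS and SES-CD: 4.
- Change in stool frequency and in abdominal pain: 2.
- Change in IBDQ: 1 (the SAP splits it into total and domain scores).
- Change in CRP and fecal calprotectin: 1 (the SAP splits it into two).

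Retained: 8 + 4 + 2 + 1 + 1 = 16. Absent: 22 − 16 = 6, and 6/22 = 27%.

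**Reconciling the SAP side.** The 16 retained items occupy 16 + 2 = 18 SAP bullets because of the two splits. The other 20 − 18 = 2 are new (IBDQ remission and IBDQ response). All 6 exploratory endpoints are new, so the SAP adds 2 + 6 = 8.

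**The six, one by one**

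| Protocol endpoint | Nearest content in the SAP |
|---|---|
| CDEIS percentage change | Absolute change only |
| SES-CD percentage change | Absolute change only |
| 75% reduction in CDEIS | CDEIS remission and response, on other criteria |
| 75% reduction in SES-CD | A >50% decrease, in a subset only (4.3.3) |
| Stool consistency | None; stool frequency only |
| Reduction in draining fistulas | Visit windows and baseline summary only |

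**Does the >50% SES-CD endpoint stand in for the 75% one?** No. Take a patient with a baseline SES-CD of 6, none of it from narrowing. A fall to 2 is 4/6 = 67%: it meets the >50% criterion and fails the 75% one, which needs 0.75 × 6 = 4.5 points, so 5 on an integer score. The population differs as well, because 4.3.3 is limited to patients above symptom and endoscopic thresholds at baseline. In the full ITT set, absolute change is the only SES-CD endpoint left, and a mean change cannot yield a proportion with a 75% reduction.

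**Was the protocol list out of date?** No. The Amendment 4 log (July 2018) records that the efficacy endpoints were edited to a by-visit form, and all six stand in the resulting text. The SAP followed about a year later.

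**The case against.** The strongest reply is that little turns on this. The primary objective is safety, there is no primary efficacy endpoint and no test, and four of the six are recalculations of scores whose absolute change is still reported. That stands, and it limits the weight of the point. It does not supply the missing tables or the missing reason.

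A reader might infer more than the documents support:

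- **That this is selective reporting.** Nothing shows a results-driven choice. The earlier analysis plan is not available, so when each endpoint dropped out is unknown. Endoscopies are read centrally by blinded reviewers (protocol 5.1.2). Keeping fistula windows and a baseline fistula table looks more like an omission than concealment. What remains is a risk that cannot be ruled out while no reason is given.
- **That the stricter endpoints were removed in favour of easier ones.** At most the two 75% reductions are strict; the other four carry no threshold. The SAP keeps mucosal healing and deep remission. It adds demanding endpoints, such as SES-CD of 4 or less with no subscore above 1, and symptom remission after at least 90 days off corticosteroids.
- **That the eight additions are themselves a fault.** Protocol 7.3.2 permits them.
- **That SAP 9.4 deliberately excludes the six.** It sits immediately before 9.5, which analyses the exploratory endpoints, and reads like an unused template heading. It matters only because it offers no route by which the six come back.

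One further objection stands in part. Neither document gives a scale or scoring rule for stool consistency. The diary-based items described in SAP 12.1 and 12.2 are liquid or soft stool counts, abdominal pain and well-being, so it is not shown that this endpoint can be derived.

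**Conclusion.** The discrepancy is real: 6 of 22 protocol efficacy endpoints have no analysis in the SAP, and no reason is recorded. Followed as written, the SAP would produce no post-baseline fistula result and no percentage-change or 75%-reduction result for either endoscopic score. It would also give nothing on stool consistency.

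The consequence is incomplete reporting against the protocol and an avoidable opening for a selective-reporting challenge. Error rates and formal inference are untouched. The documents support neither a finding of intent nor a criticism of the added endpoints. The conclusion rests on reading protocol 7.3.2 as covering the whole 5.1.1 list, which follows because the protocol designates no primary or secondary efficacy analysis. It also assumes that no separate document restores or explains the six.

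**What to change.** In SAP 4.3.2, restore by visit:

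- percentage change in CDEIS and in SES-CD;
- 75% reduction in CDEIS and in SES-CD, by OC and NRI as SAP 9.3 does for the other secondary endpoints;
- reduction in the number of draining fistulas among patients with draining fistulas at baseline, showing the number of such patients, and optionally the fistula response defined in protocol 5.1.2.

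Restore stool consistency if the diary captures it, and state how it is scored. If it does not, record the removal and the reason in SAP 11.0. Do the same for any other endpoint the sponsor decides not to restore. The protocol's own amendment log is a model: when lactoferrin was removed, it said so and said why.

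The cost is a few descriptive tables from endoscopy and fistula assessments already scheduled, with windows already defined in SAP 6.4. Only stool consistency may need a definition, or a documented removal.
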